10.1.12 Outcome

- Recovered/Resolved – Subject returned to first assessment status with respect to the AE/PTE.
- Recovering/Resolving – the intensity is lowered by one or more stages: the diagnosis or signs/symptoms has almost disappeared; the abnormal laboratory value improved, but has not returned to the normal range or to baseline; the subject died from a cause other than the particular AE/PTE with the condition remaining “recovering/resolving”.
- Not recovered/not resolved – there is no change in the diagnosis, signs or symptoms; the intensity of the diagnosis, signs/ symptoms or laboratory value on the last day of the observed study period has got worse than when it started; is an irreversible congenital anomaly; the subject died from another cause with the particular AE/PTE state remaining “Not recovered/not resolved”.
- Resolved with sequelae – the subject recovered from an acute AE/PTE but was left with permanent/significant impairment (eg, recovered from a cardiovascular accident but with some persisting paresis).
- Fatal – the AEs/PTEs which are considered as the cause of death.
- Unknown – the course of the AE/PTE cannot be followed up due to hospital change or residence change at the end of the subject’s participation in the study.

10.2 Procedures

10.2.1 Collection and Reporting of AEs

10.2.1.1 PTE and AE Collection Period

Collection of PTEs will commence from the time the subject signs the informed consent to participate in the study and continue until the subject is first administered study medication (Day 1) or until screen failure. For subjects who discontinue prior to study medication administration, PTEs are collected until the subject discontinues study participation.

Collection of AEs will commence from the time that the subject is first administered study medication (Day 1). Routine collection of AEs will continue until 30 days after the last dose of study drug.

10.2.1.2 PTE and AE Reporting

At each study visit, the investigator will assess whether any subjective AEs have occurred. A neutral question, such as "How have you been feeling since your last visit?" may be asked. Subjects may report AEs occurring at any other time during the study. Subjects experiencing a serious PTE must be monitored until the symptoms subside and any clinically relevant changes in laboratory values have returned to baseline or there is a satisfactory explanation for the change. Non-serious PTEs, related or unrelated to the study procedure, need not to be followed-up for the purposes of the protocol.

All subjects experiencing AEs, whether considered associated with the use of the study medication or not, must be monitored until the symptoms subside and any clinically relevant changes in laboratory values have returned to baseline or until there is a satisfactory explanation for the changes observed. All PTEs and AEs will be documented in the PTE/AE page of the CRF, whether or not the investigator concludes that the event is related to the drug treatment. The following information will be documented for each event:

- Event term.
- Start and stop date and time.
- Severity.
- Investigator's opinion of the causal relationship between the event and administration of study medication(s) (yes or no) (not completed for PTEs).
- Investigator's opinion of the causal relationship to study procedure(s), including the details of the suspected procedure.
- Action concerning study medication (not applicable for PTEs).
- Outcome of event.
- Seriousness.

10.2.2 Collection and Reporting of SAEs

When an SAE occurs through the AE collection period it should be reported according to the following procedure:

A Takeda SAE form must be completed and signed by the investigator immediately or within 24 hours of first onset or notification of the event. The information should be completed as fully as possible but contain, at a minimum:

- A short description of the event and the reason why the event is categorized as serious.
- Subject identification number.
- Investigator's name.
- Name of the study medication(s).
- Causality assessment.

The SAE form should be transmitted within 24 hours to the attention of the contact listed in Section 1.0.

Any SAE spontaneously reported to the investigator following the AE collection period should be reported to the sponsor if considered related to study participation.

Reporting of Serious PTEs will follow the procedure described for SAEs.

10.2.3 Reporting of Abnormal Liver Function Tests

If a subject is noted to have ALT or AST elevated $>3 \times \text{ULN}$ on 2 consecutive occasions, the abnormality should be recorded as an AE if assessed as clinically significant. In addition, an LFT Increases CRF must be completed providing additional information on relevant recent history, risk factors, clinical signs and symptoms and results of any additional diagnostic tests performed.

If a subject is noted to have ALT or AST $>3 \times \text{ULN}$ and total bilirubin $>2 \times \text{ULN}$ for which an alternative etiology has not been identified, the event should be recorded as an SAE and reported as per Section 10.2.2. The investigator must contact the Medical Monitor for discussion of the relevant subject details and possible alternative etiologies, such as acute viral hepatitis A or B or other acute liver disease. Follow-up laboratory tests as described in Section 9.1.8 must also be performed. In addition, an LFT Increases CRF must be completed and transmitted with the Takeda SAE form (as per Section 10.2.2).

10.3 Follow-up of SAEs

10.3.1 Safety Reporting of SAEs

If information is not available at the time of the first report becomes available at a later date, the investigator should complete a follow-up SAE form or provide other written documentation and fax it immediately within 24 hours of receipt. Copies of any relevant data from the hospital notes

(eg, ECGs, laboratory tests, discharge summary, postmortem results) should be sent to the addressee, if requested.

All SAEs should be followed up until resolution or permanent outcome of the event. The timelines and procedure for follow-up reports are the same as those for the initial report.

10.3.2 Safety Reporting to Investigators, IRBs or IECs, and Regulatory Authorities

The sponsor will be responsible for reporting all suspected unexpected serious adverse reactions (SUSARs) and any other applicable SAEs to regulatory authorities, including the EMA, investigators and IRBs or IECs, as applicable, in accordance with national regulations in the countries where the study is conducted. Relative to the first awareness of the event by/or further provision to the sponsor or sponsor's designee, SUSARs will be submitted within 7 days for fatal and life-threatening events and 15 days for other serious events, unless otherwise required by national regulations. The sponsor will also prepare an expedited report for other safety issues where these might materially alter the current benefit-risk assessment of an investigational medicinal product or that would be sufficient to consider changes in the investigational medicinal products administration or in the overall conduct of the trial. The investigational site also will forward a copy of all expedited reports to his or her IRB or IEC in accordance with national regulations.

11.0 STUDY-SPECIFIC COMMITTEES

No steering committee or clinical endpoint committee will be used in this study.

Takeda will designate an external hepatologist as an independent assessor of any liver enzyme elevation in the study. Takeda will also designate a Pharmacovigilance physician who is not involved in the study conduct as a sponsor liaison to participate and facilitate the safety communication between the external expert, the study site and Takeda.

All liver enzyme elevations occurring in the study subjects will be initially submitted to blinded review by the external hepatologist. The unblinded aggregate data from a series of patients will also be reviewed by the external hepatologist, a designated independent physician from the site, and a sponsor liaison before the next cohort is dosed with the support of an independent statistician, and a written assessment will be provided to Takeda liaison and the study PI in a real time.

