8.3 Randomization Code Creation and Storage

Randomization personnel of the sponsor or designee will generate the randomization schedule, which will be provided to the site pharmacist prior to the start of this study. All randomization information will be stored in a secured area, accessible only by authorized personnel.

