8.5 Unblinding Procedure

For the double-blind part of the study, the investigational drug blind shall not be broken by the investigator unless information concerning the investigational drug is necessary for the medical treatment of the subject. All study assessments and causality should be performed, if possible, prior to unblinding. In the event of a medical emergency, if possible, the medical monitor should be contacted before the investigational drug blind is broken to discuss the need for unblinding.

For unblinding a subject, the investigational drug blind can be obtained by opening sealed envelope, or contacting the dispensing pharmacist.

The sponsor must be notified as soon as possible if the investigational drug blind is broken. The date, time, and reason the blind is broken must be recorded in the source documents and the same information (except the time) must be recorded on the (e)CRF.

If any site personnel are unblinded, investigational drug must be stopped immediately and the subject must be withdrawn from the study.

No change should be made to any assessment of the subject after unblinding.

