10.1.3 Additional Points to Consider for PTEs and AEs

An untoward finding generally may:

- Indicate a new diagnosis or unexpected worsening of a pre-existing condition. (Intermittent events for pre existing conditions underlying disease should not be considered PTEs or AEs.)
- Necessitate therapeutic intervention.
- Require an invasive diagnostic procedure.
- Require discontinuation or a change in dose of study medication or a concomitant medication.
- Be considered unfavorable by the investigator for any reason.
- PTEs/AEs caused by a study procedure (eg, a bruise after blood draw) should be recorded as a PTE/AE.

Diagnoses vs signs and symptoms:

- Each event should be recorded to represent a single diagnosis. Accompanying signs (including abnormal laboratory values or ECG findings) or symptoms should NOT be recorded as additional AEs. If a diagnosis is unknown, sign(s) or symptom(s) should be recorded appropriately as a PTE(s) or as an AE(s).

Laboratory values and ECG findings:

- Changes in laboratory values or ECG parameters are only considered to be PTEs or AEs if they are judged to be clinically significant (ie, if some action or intervention is required or if the investigator judges the change to be beyond the range of normal physiologic fluctuation). A laboratory re-test and/or continued monitoring of an abnormal value are not considered an

intervention. In addition, repeated or additional noninvasive testing for verification, evaluation or monitoring of an abnormality is not considered an intervention.

- If abnormal laboratory values or ECG findings are the result of pathology for which there is an overall diagnosis (eg, increased creatinine in renal failure), the diagnosis only should be reported appropriately as a PTE or as an AE.

Pre-existing conditions:

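### Could the real-time liver assessment sent to the study PI bias later adverse-event and causality calls?

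*Protocol*

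**What the plan says.** Protocol Section 11 sets up two steps. Every liver enzyme elevation first goes to an external hepatologist for blinded review. Then, before the next cohort is dosed, "The unblinded aggregate data from a series of patients will also be reviewed by the external hepatologist, a designated independent physician from the site", together with a sponsor liaison and with support from an independent statistician. The output is described in one clause: "a written assessment will be provided to Takeda liaison and the study PI in a real time". Its content is not specified.

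The investigator's judgement enters in three places:

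- Under 10.1.3, laboratory changes "are only considered to be PTEs or AEs if they are judged to be clinically significant".
- Under 10.2.3, for ALT or AST above 3×ULN on two consecutive occasions, "the abnormality should be recorded as an AE if assessed as clinically significant".
- Under 10.2.1.2, the investigator gives a yes/no opinion on relation to study drug.

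Three protections of the blind are written down. Section 8.3 states: "All randomization information will be stored in a secured area, accessible only by authorized personnel". Section 8.4 leaves the schedule with the dispensing pharmacist. Section 8.5 asks that "All study assessments and causality should be performed, if possible, prior to unblinding" and adds: "No change should be made to any assessment of the subject after unblinding".

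SAP 7.12 plans no formal interim analysis. It names the hepatologist and the liaison but not the unblinded aggregate review. SAP 7.11.1 tabulates treatment-emergent events by relationship and intensity. SAP 7.11.2 tabulates numeric laboratory change, shifts against the normal range and markedly abnormal values.

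**The concern.** Section 6.2 explains that placebo control was added because ALT and/or AST rose in 15 of the first 16 open-label subjects, 7 of them above ULN, and a drug effect had to be excluded. Section 11 takes care to seat independent people in the unblinded review, then sends their conclusion to the one person meant to stay outside it. The PI already sees each subject's ALT and AST. If the assessment conveyed that rises were concentrated on active drug, the PI could become readier to call a rise clinically significant and drug-related.

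The rises seen so far are the kind where judgement decides. None exceeded 3×ULN on Day 11, so the more prescriptive rule in 10.2.3 would not have applied. Section 8.5 is written for breaking the code of a single subject and does not plainly reach first-time calls in later cohorts. At stake are the liver-laboratory entries in the AE, intensity and drug-related tables. The type I error is not at stake, since SAP 7.1.1 plans no formal test.

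**Working it through.** The plan states no figure to reproduce on this point. The check asks what the PI could learn, and what that could do to each output.

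**1. Inputs.** Double-blind part: 16 per arm, 48 in total, so 32/48 = 2/3 are on active drug (Section 6.1). Open-label subjects above ULN on Day 11: 7/16 = 43.8%, exact 95% CI 19.8% to 70.1% (count from Section 6.2). The number of double-blind cohorts is not given.

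**2. What aggregate knowledge reveals about one subject.** With rise rates p_A on active and p_P on placebo, and 2:1 active to placebo,

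P(active | rise) = 2·p_A / (2·p_A + p_P).

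Take p_A = 0.4375; the placebo rates are assumptions.

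| p_P | P(active given a rise) |
|---|---|
| 0.4375 | 0.875/1.3125 = 0.67 |
| 0.20 | 0.875/1.075 = 0.81 |
| 0.10 | 0.875/0.975 = 0.90 |
| 0 | 1.00 |

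An aggregate result could therefore strengthen a guess. Only the extreme statement, that no placebo subject had a rise, identifies anyone, and then only in the cohort already reviewed. Such a pattern can also arise by chance. If rises are unrelated to treatment, the probability that 4 subjects with rises are all on active is C(8,4)/C(12,4) = 70/495 = 14.1% in a cohort of 12, and 17.1% or 18.5% for cohorts of 24 or 48 (assumed sizes).

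**3. What it does to the comparison of arms in later cohorts.** Let c_k be the probability that the PI calls a given rise an AE in cohort k. Two subjects with the same rise look alike to a PI without allocations, so c_k is common to both arms. The expected liver-AE count in arm j is Σ c_k·n_jk·p_j. Randomization makes the expected cohort sizes proportional across arms, so:

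- ratio of AE rates = p_A/p_P, whatever the c_k;
- difference in AE rates = c·(p_A − p_P), where c is the average call probability.

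If the drug has no effect, p_A = p_P and the expected difference is zero for every c. If it has one, say p_A = 0.4375 and p_P = 0.20 (assumed), the ratio is 2.19 throughout. Doubling c from 0.2 to 0.4 moves the difference from 0.2 × 0.2375 = 4.8 to 9.5 percentage points. The same holds for the yes/no causality opinion, with its own factor. If the call depends on the size of the rise, the ratio may move somewhat, but one rule still applies to both arms.

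**4. How many calls could be touched.** With k equal cohorts (assumed), 48(k−1)/k subjects are dosed after the first assessment, of whom 32(k−1)/k are on active.

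- k = 2: 24 subjects, 16 active, 16 × 0.4375 = 7.0 expected above ULN.
- k = 6: 40 subjects, 26.7 active, 26.7 × 0.4375 = 11.7 expected above ULN.

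These are ceilings. A rise becomes an AE only if judged clinically significant, and 10.1.3 says that retesting and monitoring do not count as intervention. The rate of 7/16 may not carry over either: Amendment 4 lowered dietary fat from about 30% to about 20% of calories, and Section 6.2 lists diet as a possible cause.

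**5. What stays outside the PI's judgement.** ALT/AST change from baseline, the shift table and the markedly abnormal counts (above 3×ULN, SAP Appendix A) come from laboratory values. A rise above ULN from a normal baseline appears in the shift table whether or not anyone calls it an AE. The PK endpoints come from assayed concentrations.

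**The case for a change.** The strongest opposing case is that the restriction costs one sentence, that the protocol writes such a restriction for monitoring in 14.1, and that restricted codes protect allocations but not conclusions. No clinical endpoint committee is used, so nothing replaces the investigator's entry. The blinded case review is only a partial second opinion, because the same hepatologist later sees the aggregates. In the reviewed cohort some calls may still be open when the assessment arrives, since rises above ULN are followed until they resolve. A PI might also guess allocation from blood pressure, which the drug lowers.

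Much of this is true as a description. The text is silent, and a careless assessment could say too much. But the silence sits inside an arrangement whose evident purpose is a firewall: an external expert, a site physician other than the PI, a liaison outside study conduct and an independent statistician. People in those roles would ordinarily send the PI a safety conclusion, not results by arm. Clues from blood pressure exist with or without the assessment. Strong expectation exists too, because Section 6.2 already reports the open-label rises and Section 6.1 states the two-in-three chance of active drug. Section 8.5 already sets the principle that calls come before unblinding and are not revised afterwards. Its withdrawal sentence concerns a subject whose code is broken, so no contradiction with an aggregate review is shown.

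**Conclusion.** The observation is accurate, but it describes missing detail, not a rule that gives a wrong result. Followed as written, the plan answers the liver question from numeric laboratory data and the PK question from concentrations, and neither depends on what the PI is told. What remains is possible influence on liver-laboratory entries in descriptive AE and causality tables. Without allocations that influence is shared by all arms, so it changes how many rises are called events and cannot by itself manufacture a difference between drug and placebo. Its size cannot be estimated while cohort number and content of the assessment are unknown; 7.0 to 11.7 active subjects with a rise is a ceiling under assumed cohorts and an unchanged 7/16 rate.

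This conclusion assumes that the reviewers send the PI no arm-level or subject-level treatment information, which is the natural reading of Section 11. If an assessment did disclose such information, the clinical study report should say so, and liver AE and causality tables for the affected cohorts should be read with caution beside the laboratory summaries. SAP 7.12's omission of the aggregate review is likewise missing detail. Reopening text written to meet the Ethics Committee's request would change no planned result.

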12.0 DATA HANDLING AND RECORDKEEPING

The full details of procedures for data handling will be documented in the Data Management Plan. AEs, PTEs, medical history, and concurrent conditions will be coded using the Medical Dictionary for Regulatory Activities (MedDRA). Drugs will be coded using the World Health Organization (WHO) Drug Dictionary.

12.1 (e)CRFs

Completed (e)CRFs are required for each subject who signs an informed consent.

The sponsor or its designee will supply investigative sites with access to (e)CRFs. These forms are used to transmit the information collected in the performance of this study to the sponsor and regulatory authorities. (e)CRFs must be completed in English.

After completion of the entry process, computer logic checks will be run to identify items, such as inconsistent dates, missing data, and questionable values. Queries may be issued by Takeda personnel (or designees) and will be answered by the site.

Corrections to (e)CRFs are recorded in an audit trail that captures the old information, the new information, identification of the person making the correction, the date the correction was made, and the reason for the change. Reasons for significant corrections should additionally be included. All new additions are to be made with the date and signature.

The principal investigator must review the (e)CRFs for completeness and accuracy and must sign and date the appropriate (e)CRFs as indicated. Furthermore, the investigator must retain full responsibility for the accuracy and authenticity of all data entered on the (e)CRFs.

After submission of the (e)CRFs to the sponsor, any change of, modification of, or addition to the data on the (e)CRFs should be made by the investigator with use of change and modification records of (e)CRFs (Data Clarification Form) provided by the sponsor. The principal investigator must review the Data Clarification Form for completeness and accuracy, and must sign, and date the form.

(e)CRFs will be reviewed for completeness and acceptability at the study site during periodic visits by study monitors. The sponsor or its designee will be permitted to review the subject's medical and hospital records pertinent to the study to ensure accuracy of the (e)CRFs. The completed (e)CRFs are the sole property of the sponsor and should not be made available in any form to third parties, except for authorized representatives of appropriate governmental health or regulatory authorities, without written permission of the sponsor.

12.2 Record Retention

The investigator agrees to keep the records stipulated in Section 12.1 and those documents that include (but are not limited to) the study-specific documents, the identification log of all participating subjects, medical records, temporary media such as thermal sensitive paper should be copied and certified, source worksheets, all original signed and dated informed consent forms, subject authorization forms regarding the use of personal health information (if separate from the

informed consent forms), electronic copy of (e)CRFs, including the audit trail, and detailed records of drug disposition to enable evaluations or audits from regulatory authorities, the sponsor or its designees. Any source documentation printed on degradable thermal sensitive paper should be photocopied by the site and filed with the original in the subject's chart to ensure long-term legibility. Furthermore, International Conference on Harmonization (ICH) E6 Section 4.9.5 requires the investigator to retain essential documents specified in ICH E6 (Section 8) until at least 2 years after the last approval of a marketing application for a specified drug indication being investigated or, if an application is not approved, until at least 2 years after the investigation is discontinued and regulatory authorities are notified. In addition, ICH E6 Section 4.9.5 states that the study records should be retained until an amount of time specified by applicable regulatory requirements or for a time specified in the Clinical Study Site Agreement between the investigator and sponsor.

Refer to the Phase 1 Site Specifications document for the sponsor's requirements on record retention. The investigator should contact and receive written approval from the sponsor before disposing of any such documents.

